4. Currently enrolled or planning to enroll in a potentially confounding clinical study during the course of the study (co-enrollment in concurrent studies is only allowed when documented pre-approval is obtained from the Medtronic study manager (or designee))
5. Pregnant or is of child-bearing potential and unwilling to use a medically acceptable form of birth control during the study
6. Has untreated major psychiatric comorbidity, as determined by the investigator, or designee
7. Has serious drug-related behavioral issues (e.g., alcohol dependency, substance abuse), as determined by the investigator, or designee
8. Has unresolved major issues of secondary gain (ie, secondary reason not to report improvement in health condition), as determined by the investigator, or designee

Inclusion criterion – baseline visit

To proceed on with the Baseline visit, the subject must meet the following inclusion criteria:

1. Has an average overall VAS pain score ≤ 4 based on the Baseline diary

Exclusion criteria – baseline visit

[figure not shown]
To proceed on with the Baseline visit, the subject must not meet any of the following exclusion criteria:

1. Has provided response to Baseline SSA as “Neutral”, “Somewhat unsatisfied”, or “Very unsatisfied” with the therapy
2. Completed less than 5 of the 7 days of the Baseline diary

The overall study duration, from first subject enrollment to last subject visit, is expected to last approximately 15 months. Each subject’s participation in the study is expected to last approximately 12 weeks from enrollment. The completion of the study is defined as the approval of the Final Study Report and closure of all sites.

A summary of the study design is illustrated in Figure 1.

Figure 1: Study Visit Diagram

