7.4. Handling of Missing, Unused, and Spurious Data and Dropouts

Missing data are a potential source of bias when analyzing study data. A rigorous study design and execution will help prevent the incidence of missing data from occurring.

The analysis of the primary and secondary objectives will use subjects who provide data. The purpose of the study is to characterize the minimum amplitude that maintains SCS therapy satisfaction and overall pain relief; in case subjects drop out during follow-up, the percentage of amplitude prior to dropout will be used to summarize the minimum amplitude.

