7.9.1.2. Experimental Design

The measurement of SSA is described in Section 5.2.1.1. Subject dissatisfaction with the therapy is defined as subjects choosing either 'somewhat unsatisfied' or 'very unsatisfied'. The SSA is collected at baseline and scheduled follow-up visits.

A large black rectangular redaction box covers the bottom portion of the page.

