7.9.1.3. Analysis Methods and Presentation Format

The frequency and percentage of subjects satisfied with the therapy will be summarized at baseline and scheduled follow-up visits. In case subjects drop out during follow-up, a category of missing data will be included in the summary so that the percentage is not inflated because of missing data. As an additional analysis, if a subject drops out of the study due to dissatisfaction with the therapy, the subject will be treated as dissatisfied (same level at dropout) at the subsequent lower percentages of amplitude where data was not collected

The percentage of amplitude from perception threshold for maintaining subjects' satisfaction with the therapy will be summarized too. In case subjects drop out during follow-up, the percentage of amplitude prior to subject dropout will be used as the minimum amplitude in the summary.

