7.9.2.3. Analysis Methods and Presentation Format

The mean and standard deviation of the pain scores (including overall, back, and leg pain) will be summarized at each follow-up visit. The change in pain scores will be summarized too. As an additional analysis, if a subject drops out of the study due to dissatisfaction with the therapy, the subject's pain scores at dropout will be used at the subsequent lower percentages of amplitude where data was not collected

The percentage of amplitude from perception threshold for maintaining overall pain relief will be summarized. In case subjects drop out during follow-up, the percentage of amplitude prior to subject dropout will be used as the minimum amplitude in the summary.

In addition, a repeated measure analysis may be applied to examine the relationship between the change in pain score and percent amplitude. The dependent variable will be the change in pain score,

the independent variables will be percent amplitude and visit as fixed effects, and subject as the random effect. The interaction term of percent amplitude by visit will be tested and kept out of the model if it is not significant.

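### As visibly worded, the dropout rule for the minimum amplitude enters upper bounds as exact values and, depending on what *prior to* means, can enter a setting that failed or leave a treated subject with no value

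*SAP*

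**What the plan says.** SAP 7.9.1.3 ends with the rule for the primary summary: when a subject drops out, "the percentage of amplitude prior to subject dropout will be used as the minimum amplitude in the summary". SAP 7.9.2.3 repeats the sentence for the secondary objective, and SAP 7.4 gives it in general form: "the percentage of amplitude prior to dropout will be used to summarize the minimum amplitude". In the visible text, dropping out is the only trigger. Part of SAP 7.9.1.2, just before the primary rule, is blacked out and may define terms; nothing is claimed about it.

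Neighbouring outputs treat dropouts differently:

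- In the percent-satisfied table, "a category of missing data will be included in the summary so that the percentage is not inflated because of missing data".
- In an additional analysis of exits for dissatisfaction, "the subject will be treated as dissatisfied (same level at dropout) at the subsequent lower percentages of amplitude".
- In the matching pain analysis of SAP 7.9.2.3, the subject's "pain scores at dropout will be used at the subsequent lower percentages of amplitude where data was not collected".

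SAP 7.9.1.4 and 7.9.2.4 assign both objectives to the treated analysis set, which takes in anyone given even one setting, so a subject who received only 80% belongs to it. The Protocol (13.1.3, 13.3.4, 13.4.4) limits the analysis to those with data and has no dropout rule for the minimum.

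The data needed for a better rule are planned: an SSA on each completed setting (Protocol 9.4.3), optional final-visit procedures at early exit, and a recorded exit reason (both Protocol 9.10).

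**The concern.** The primary result is the distribution of the lowest setting that maintains satisfaction. Settings fall in a fixed order (80, 60, 40, 20% of perception threshold), and Protocol 10.1.1.6 names insufficient pain relief as a possible reason to withdraw. Some exits can therefore be expected at settings that have failed, which is where the meaning of *prior to* matters.

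A subject who leaves for an unrelated reason while still satisfied raises a different problem. That subject shows only that the minimum is at or below the last setting that worked. The rule nevertheless enters one value, and nothing visible marks it as a bound.

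The percent-satisfied table and the summary of discontinuation reasons would let a reader suspect a problem, but not correct the distribution. Independent programming of the primary analysis (Level I, SAP 8) would probably reveal two readings without saying which is right. The secondary code gets Level II validation: code review plus, where appropriate, manual calculations or simple programming checks.

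**Working it through.** The plan gives no figure to reproduce. The check has three steps.

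**1. Three readings**

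- A: the setting in use at exit.
- B1: the setting before that one, taken literally.
- B2: as B1, but recorded SSA responses are kept, so a setting rated as failing is never entered.

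| History | A | B1 | B2 | What is known |
|---|---|---|---|---|
| Satisfied at 80 and 60; leaves because 40 failed | 40 | 60 | 60 | 60 |
| Satisfied at 80, dissatisfied at 60; leaves during 40 | 40 | 60 | 80 | 80 |
| Satisfied at 80 and 60; unrelated exit during 40, no SSA | 40 | 60 | 60 | at or below 60 |
| Leaves during 80 because it failed | 80 | no value | no value | not maintained at 80 |

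In the first row, A records the subject as maintained at 40%, while the additional analysis in the same SAP section counts that subject as dissatisfied.

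**2. Count of path types, without rates**

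Take five true minima (none, 80, 60, 40, 20) by four exit periods, which gives 20 paths. Response is assumed monotone in amplitude.

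| Outcome | A | B1 | B2 |
|---|---|---|---|
| Failing setting entered | 10 | 6 | 0 |
| No value (exit during 80%) | 0 | 5 | 5 |
| Bound entered as exact | 9 | 6 | 6 |

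These are kinds of path, not probabilities.

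**3. Illustration on assumed rates**

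At n = 40, one wrong value moves a share by 1/40 = 2.5 points. Anything further needs assumptions that the documents do not supply. Assume true minima of none/80/60/40/20 in 10/20/25/20/25% of subjects. Assume that per period a subject leaves for unrelated reasons with probability u = 2% and, if dissatisfied, also with independent probability d = 10%. The exit probability is then 0.02 when satisfied and 1 − 0.98 × 0.90 = 0.118 when not. The true share with a minimum of 40% or lower is 20 + 25 = 45%.

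- A adds failing subjects who leave during 40% or 20%, and loses satisfied ones who leave during 80% or 60%. With 1 − 0.882² = 0.2221: 45 + 10 × 0.882² × 0.2221 + 20 × 0.98 × 0.882 × 0.2221 + 25 × 0.98² × 0.2221 − 45 × (1 − 0.98²) = 45 + 1.73 + 3.84 + 5.33 − 1.78 = 54.1%.
- B1 adds failing subjects who leave during 20%, and loses satisfied ones who leave during 80%, 60% or 40%: 45 + 10 × 0.882³ × 0.118 + 20 × 0.98 × 0.882² × 0.118 + 25 × 0.98² × 0.882 × 0.118 − 45 × (1 − 0.98³) = 45 + 0.81 + 1.80 + 2.50 − 2.65 = 47.5%.
- B2 has the losses only: 45 − 2.65 = 42.4%.
- Implied total dropout: 10 × (1 − 0.882⁴) + 20 × (1 − 0.98 × 0.882³) + 25 × (1 − 0.98² × 0.882²) + 20 × (1 − 0.98³ × 0.882) + 25 × (1 − 0.98⁴) = 3.95 + 6.55 + 6.32 + 3.40 + 1.94 = 22.2%, or 8.9 of 40.

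Of 40 subjects (A/B1/B2), 7.1/3.6/0 have a failing setting entered, 1.6/1.1/1.1 a bound entered as exact, and 0/1.2/1.2 no value.

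The same formulas at other rates:

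| d / u | A | B1 | B2 | Implied dropout |
|---|---|---|---|---|
| 5% / 0% | 50.2 | 47.5 | 45.0 | 8% |
| 5% / 5% | 49.5 | 42.8 | 38.6 | 25% |
| 10% / 2% | 54.1 | 47.5 | 42.4 | 22% |
| 20% / 0% | 62.1 | 52.6 | 45.0 | 29% |
| 20% / 5% | 58.7 | 46.4 | 38.6 | 42% |

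**The case against.** The best defence is that the context points to B2. SAP 7.4 is a missing-data section; such a rule fills gaps, and nothing says that it overrides a recorded SSA. In SAP 7.9.1.3 the sentence follows directly on the amplitude that maintains satisfaction, which a failing setting does not. The dissatisfaction analysis alongside it is fair evidence against A. Under B2 no failing setting is entered, and what remains in the middle case is about 1.1 bounds and 1.2 subjects without a value among 40. Of those 1.2, about 0.5 (40 × 10% × 0.118) have no minimum at all, so an empty cell is not wrong for them. Under A, 3 of the 9 bound paths happen to record the correct number.

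Most of this stands. B2 is the reading most consistent with context and may be what was intended, but the visible SAP does not say so. Nor does it remove the bound problem.

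It can also be said that "The analysis of the primary and secondary objectives will use subjects who provide data" disposes of early exits without data. It may, but SAP 7.9.1.4 puts those subjects in the population for this analysis, and the SAP does not say whether they leave the denominator.

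Finally, this is a descriptive feasibility study, and other tables would show the dropouts. That limits the harm but does not make the distribution right.

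**Conclusion.** The concern holds for the visible text. Under every reading, subjects who leave while still meeting the criterion can be entered with an exact minimum above 20% when only an upper bound is known. Entry of a failing setting depends on A or B1. The missing value for an exit during 80% depends on B1 or B2.

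A reader might infer more than the documents support:

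- *That the plan will count failures as successes.* This follows only from A or B1, and the documents do not fix the reading.
- *That the SAP sets no condition anywhere.* This can be said only of the visible text, because part of SAP 7.9.1.2 is blacked out.
- *That the primary share will be overstated by about 9 points* (54.1 against 45). That figure rests on an assumed distribution of minima and assumed exit rates, with implied dropout of 22% in the middle case and up to 42%. The documents support none of these, and under B2 the share is never overstated in the cases shown.

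What can be stated without assumed rates is the logic of the rule and the 2.5 points per wrong value at n = 40. No test, alpha or power is affected; the harm is a misreported distribution for the primary and secondary objectives. It should be corrected before analysis.

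**What to change.** In SAP 7.4, 7.9.1.3 and 7.9.2.3, replace the sentence with wording such as:

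> For subjects who drop out, the minimum amplitude is the lowest setting that met the criterion (SSA for the primary objective, change in average overall VAS for the secondary) before the first setting that did not. A recorded failing value is never overridden. If no value was recorded for the setting in use at exit, exit for dissatisfaction with therapy or insufficient pain relief counts as not maintained at that setting. Subjects who leave with no failing setting, and whose last setting that met the criterion is above 20%, are tabulated as at or below that setting. Subjects failing at 80% are tabulated as not maintained at 80%. Subjects who leave during 80% for any other reason with no data are tabulated as not assessed. All treated subjects stay in the denominator.

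Apply the same definition, before the first failing setting, to completers unless the blacked-out text already gives one. It also settles a satisfied response that follows a dissatisfied one.

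In the middle illustration, with no exit SSAs, this would report 42.4% confirmed at 40% or lower plus 5.0% undetermined. The range of 42.4 to 47.4% contains the assumed true 45%.

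The cost is wording in three sections and minor programming, using SSA, VAS and exit reasons already collected; no extra subjects, visits or forms. The downside is that some subjects carry a bound or *not assessed* instead of a value, and the reported minimum may look less favourable.

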7.9.1.4. Determination of Subject for Analysis

Subjects who proceed beyond the baseline visit and receive at least one programmed amplitude setting (treated analysis set).

7.9.2. Secondary Objective

To characterize the minimum amplitude as a percentage from perception threshold that maintains overall pain relief. Maintaining overall pain relief is defined as having ≤ 2 points increase in average overall pain VAS during study follow-up.

7.9.2.1. Hypothesis

There is no hypothesis testing for the secondary objective. The purpose of the secondary objective is to characterize the minimum amplitude that maintains overall pain relief of equal or less than 2 points increase in average overall VAS pain scores.

7.9.2.2. Experimental Design

The measurement of pain score is described in Section 5.2.1.2. For baseline, an average overall VAS pain score is calculated using all 7 days of the diary. For scheduled follow-up visits, an average overall VAS pain score is calculated using the last 3 days of the diary prior to the scheduled visit, to ensure that there is no residual treatment effect from the previous period. The pain scores are collected at baseline and scheduled follow-up visits.

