5.2.2. Safety measures

Safety will be evaluated by the collection of device deficiencies and adverse events related to the following:

- The implanted SCS system and accessories
- Spinal cord stimulation therapy

6. Determination of Sample Size

An estimated 60 subjects will be enrolled in order for at least 40 subjects to proceed beyond the Baseline visit. A sample size of 40 subjects is reasonable to characterize the distribution of the minimum amplitude as a percentage of perception threshold that maintains SCS therapy satisfaction, as well as to provide data for consideration of future studies.

[Redacted]

7. Statistical Methods

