7.7. Treatment Characteristics

Subjects are implanted before enrolling into the study, so the surgical procedures are not described in the study. The neurostimulator and lead(s) model will be summarized. Subjects proceed beyond baseline visit will receive 4 different programmed amplitude setting in the following order: 80%, 60%, 40%, and 20% of perception threshold amplitude, each for approximately two weeks. Subject assessments are collected at each following up visit.

Subjects' pain medications will be collected. All pain medications will be coded using the appropriate version of the World Health Organization (WHO) Drug Dictionary at the appropriate Anatomical Therapeutic Chemical (ATC) level.

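### The Baseline diary is both the VAS ≤ 4 entry filter and the reference for the 2-point rise, so regression to the mean adds modestly to apparent loss of relief at every amplitude

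*SAP*

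**What the plan says.** SAP 5.1 sets the Baseline entry rule: "Has an average overall VAS pain score ≤ 4 based on the Baseline diary". Subjects are also stopped there if either of two exclusions applies: "Has provided response to Baseline SSA as “Neutral”, “Somewhat unsatisfied”, or “Very unsatisfied” with the therapy" or "Completed less than 5 of the 7 days of the Baseline diary".

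SAP 7.9.2.2 then takes the reference from the same diary: "For baseline, an average overall VAS pain score is calculated using all 7 days of the diary". The follow-up score is an average "using the last 3 days of the diary prior to the scheduled visit". Protocol 13.4.2 says the same.

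SAP 7.9.2 sets the classification: "Maintaining overall pain relief is defined as having ≤ 2 points increase in average overall pain VAS during study follow-up". SAP 7.7 gives the settings in fixed descending order: "80%, 60%, 40%, and 20% of perception threshold amplitude, each for approximately two weeks".

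Protocol 9.4.1 lists no VAS at Screening, so no earlier score exists that played no part in entry. The readable text of SAP 7.9.2.3 summarizes pain scores, their change and the minimum amplitude. It also allows an optional repeated-measures model of change on percent amplitude, visit and subject. Nothing readable mentions regression to the mean or a second reference.

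**The concern.** A subject whose usual pain is about 4.5 gets in only after a good week. That good week becomes the reference, and later scores tend to return to 4.5 whatever the amplitude. Unless the Baseline and follow-up averages are perfectly correlated, selecting low Baseline averages makes the expected later change positive.

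The secondary result classifies each subject against a fixed 2-point line and then reports the lowest amplitude at which relief held. An offset common to all four settings cancels when settings are compared, but not against a fixed line. It moves some subjects over the line and pushes the reported minimum amplitude upward. It matters most at 80%, the first step, where a rise from Baseline is easily read as lost efficacy.

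**Working it through.** **Inputs from the documents.** Entry cut 4 (SAP 5.1); reference a 7-day mean and follow-up a 3-day mean (SAP 7.9.2.2); margin 2 points (SAP 7.9.2); 40 of 60 proceeding, from SAP Section 6: "An estimated 60 subjects will be enrolled in order for at least 40 subjects to proceed beyond the Baseline visit". The planned pass fraction is 40/60 = 0.667. The plan states no precision or SD behind the 40, so it has no figure to reproduce.

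**Inputs assumed.** SDs, correlations and usual VAS level. The documents give none of these.

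**Step 1: normal approximation at the planned pass fraction.** With no amplitude effect and equal SDs at both times, the expected rise among those admitted is

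(1 − ρ) × SD × φ(a)/Φ(a).

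For Φ(a) = 0.667, a = 0.431, φ(a) = 0.3636 and φ(a)/Φ(a) = 0.545.

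- SD 1.5, ρ 0.9: 0.1 × 1.5 × 0.545 = 0.08 points.
- SD 2.0, ρ 0.7: 0.3 × 2.0 × 0.545 = 0.33 points.
- SD 2.5, ρ 0.6: 0.4 × 2.5 × 0.545 = 0.55 points.

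The share rising more than 2 points, selected against unselected, is 0.2% v 0.1%, 13.0% v 9.8% and 24.5% v 18.5% respectively. Selection adds about 0.1 to 6 percentage points.

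**Step 2: diary model.** Score = subject mean + week effect + daily error, clipped to 0–10. Baseline is a 7-day mean kept if ≤ 4; follow-up is a 3-day mean; there is no true change. The usual mean was set so that about two-thirds pass.

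| | Lower noise | Higher noise |
|---|---|---|
| Usual mean VAS | 3.2 | 3.1 |
| SD between subjects / week / day | 1.5 / 0.7 / 1.0 | 1.5 / 1.3 / 1.5 |
| Pass Baseline | 68% | 67% |
| Mean spurious rise | 0.19 | 0.52 |
| Rise > 2, selected | 5.5% | 19.5% |
| Rise > 2, no selection | 4.3% | 14.8% |
| Added by selection | 1.2 points | 4.7 points |
| Of 40 subjects | 0.012 × 40 = 0.5 | 0.047 × 40 = 1.9 |

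Hand check of the mean rise, ignoring clipping. The part of the Baseline variance that does not carry over is week variance + day variance/7, so the rise is that amount divided by the Baseline SD, times φ/Φ.

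- Lower noise: 0.49 + 1.00/7 = 0.633; Baseline SD = √(2.25 + 0.633) = 1.70; a = (4 − 3.2)/1.70 = 0.47; φ/Φ = 0.52; rise = 0.633/1.70 × 0.52 = 0.19.
- Higher noise: 1.69 + 2.25/7 = 2.011; Baseline SD = √(2.25 + 2.011) = 2.06; a = (4 − 3.1)/2.06 = 0.44; φ/Φ = 0.54; rise = 2.011/2.06 × 0.54 = 0.53.

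**Step 3: where the false losses come from.** Without selection, 4.3/5.5 = 78% and 14.8/19.5 = 76% of them would still occur. That is week-to-week and day-to-day noise. The 3-day follow-up mean enlarges it: daily variance enters as one third, against one seventh for a 7-day mean.

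**Step 4: the 80% period as reference.** Its diary was not used for entry. Measured against it, the mean null change is 0.0 and the share rising more than 2 points is about 5 to 15%. The selection offset is gone and the noise remains.

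**Step 5: what happens if both references must agree.** Lower-noise SDs, usual mean 3.2. With a true rise of 1.5 points at 80% and 3 points at 60%, the Baseline rule finds loss at 60% in 84% of subjects; requiring both references to agree finds it in about one third. If the full 3 points are already present at 80%, detection at 60% falls from 84% to 6%.

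**The case against.** The strongest reply is that this is small and partly mitigated. Baseline runs at least two weeks on one fixed program, the reference averages up to seven days, pain medication must be stable, and the 2-point margin is several times the mean shift. The 40 of 60 also covers failures on satisfaction and diary completion, so selection on VAS may be weaker than modelled, although the satisfaction filter may add some selection of its own. With SD 1.5 and correlation 0.9 the excess is negligible. The study is descriptive, with no hypothesis test, and mean pain at the 80% visit will be reported anyway.

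Most of that stands, and it limits the size. It does not remove the direction. Having no test does not excuse bias in a descriptive estimate, and group means do not correct a per-subject classification.

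A reader might infer that regression to the mean creates the loss seen at 80%, or accounts for most of it. The documents do not support that: they give no variance figures, and in the modelled cases about three-quarters of false losses occur without selection. Larger figures need a stricter filter than the plan expects. For example, a usual mean of 4.0 with the higher-noise SDs gives a rise of 0.77 and 24.6% v 16.0%, but only half of subjects pass.

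**Conclusion.** The point holds as a modest upward bias. One diary serves as filter and reference, and the readable text does not separate the two roles. At about the planned pass fraction the spurious mean rise is about 0.2 to 0.5 points, and selection adds about 1 to 5 percentage points, or 0.5 to 2 of 40 subjects, to false loss at a visit. Every SD, correlation and usual VAS level behind these figures is assumed.

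Contrasts between amplitudes are little affected if the correlation with Baseline is the same for all periods. If it decays with time, the offset would grow in the later, lower-amplitude periods.

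A reader might also infer that the 80% period is a clean no-change control. It is not: the documents do not hold subjects at their entry amplitude after Baseline, so a rise at 80% may be real.

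**What to change.** In SAP 7.9.2.3:

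1. Keep the Baseline-referenced analysis as the main result.
2. Add a supplementary table giving change, and the ≤ 2-point classification, at 60, 40 and 20% against each subject's own 80%-period 3-day average.
3. State that the Baseline-to-80% change mixes regression to the mean from the entry rule with any real effect of leaving the entry amplitude.
4. Do not require the two references to agree before calling relief lost; Step 5 of the working shows how much true loss that would hide.

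The cost is one table and a sentence or two, from data already collected, with no change to visits or conduct. The drawback is that the 80% reference is a noisier 3-day mean and cannot show relief already lost at 80%, so it can only supplement the main result. Settling this before analysis avoids choosing a reference after seeing the data.
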